4.6 Data analysis

When the target number of patients has been enrolled (see below), and a sufficient number (84 in each arm) have completed the full 3-year induction, the following analyses between the transdermal and oral groups will be conducted:

- Demographics of patients choosing oral or transdermal estradiol preparations, differences at baseline
- Numbers of patients in each treatment arm, their centres and countries
- Adherence to each of the treatment arms including % of dropouts
- Propensity score matching to reduce bias due to confounding factors e.g. 45,X karyotype, midparental height, height at the beginning of pubertal induction, duration of prior GH treatment, GH responsiveness and treatment or not with oxandrolone.
- Use of Directed Acyclic Graphs to establish the minimally sufficient set of confounders for each outcome parameter, entering these into multivariable regression models

The minority of girls undergoing a 2-year induction will be analysed separately and their outcomes compared with the majority of girls undergoing the full three-year induction

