Study Design	Pragmatic comparative open study comparing oral and transdermal pubertal induction
Study Participants	Girls with Turner syndrome aged ≥11.0 years requiring pubertal induction
Planned Size of Sample	84 patients in each treatment arm – transdermal and oral = 168 total
Follow up duration	Follow up will be for at least the duration of induction: 3 years in most girls, 3 ½ years in especially short girls, and 2 years in the case of older girls receiving a shortened induction protocol. However, where possible, follow up will be continued until final adult height is achieved (usually around 16 years)
Planned Study Period	Eight years (including set-up and recruitment)
Research Question/Aim(s)	Is transdermal induction of puberty in girls with Turner syndrome superior to oral induction in terms of:
	Height gain during the 3-year induction period? This is the primary outcome measure

	Adult height, cardiovascular health (systolic blood pressure, aortic root dilatation), uterine health (uterine shape and size), bone health (bone mineral density), patient satisfaction and acceptability (adherence to each regime). These are secondary outcome measures
Brief synopsis of study	Most girls with Turner syndrome (TS) require pubertal induction with estrogen, followed by long term replacement. However, no adequately powered prospective studies comparing transdermal with oral 17β - estradiol administration exist. This reflects the difficulty of securing funding to study a rare condition with relatively low morbidity/mortality when competing against conditions such as cancer and vascular disease.
	The TS Working Group of the European Society for Paediatric Endocrinology (ESPE) has reached a consensus for two 3-year pubertal inductions regimens – one transdermal and one oral. A shorter regimen for the minority of girls presenting aged >14 years has also been devised.
	Prerequisites include suitable 17β-estradiol tablets and matrix patches to allow the delivery of incremental doses based on body weight.
	We wish to carry out an international prospective cohort study with single centre analysis in which clinicians and families are invited to choose either of the agreed regimens, usually starting at 11 years. We hypothesise that pubertal induction with transdermal estradiol will result in better outcomes for some key parameters.

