3.2 Outcomes

The primary outcome measure is height gain in cm during the pubertal induction period, since this can be accurately determined in the context of an international framework. Secondary outcome measures include final adult height, systolic blood pressure, aortic root diameter, uterine size and shape, bone mineral density, adherence and dropout rate.

Table 1 Outcome measures to be analysed at the end of pubertal induction in girls with Turner syndrome using either an oral (see Tables 2a and 2b) or transdermal (see Tables 3a and 3b) 17- β estradiol regimen approved by the Turner Syndrome Working Group of ESPE.

Induction period is normally 3 years (plus 6 months for very short girls), exceptionally 2 years for girls presenting late (e.g. >14 years), minimum follow up is during induction period but where possible, follow up is to final adult height.

Primary outcome measure

Pubertal height gain, i.e. increase in height in centimetres during the (usually) 3-year pubertal induction period

Secondary outcome measures

- Final adult height in centimetres & population-specific SDS
- Change in population-specific height SDS between start and end of pubertal induction
- Breast development (clinical assessment)
 - Tanner B4-5 reached
 - Satisfactory breast shape (ie not tubular, no overdevelopment of areolae) according to attending clinician (graded as satisfactory or unsatisfactory)
- Cardiovascular health
 - Systolic & diastolic blood pressure at the end of induction (lowest of three readings or mean values if recorded by ambulatory 24-hour blood pressure monitoring
 - Change in aortic root diameter and aortic size index between start and completion of induction
- Patient satisfaction; adherence/compliance with treatment
 - Percentage drop-outs from either regimen
 - Average of good, reasonable and poor rating with adherence during pubertal induction (3 years ± X months)
 - Patient satisfaction with shape and size of breast (scoring 1-5 where 5=best)
 - Patient satisfaction with mode of administration (scoring 1-5 where 5=best)
- Uterine health and sex hormone profile at the end of induction
 - Uterine length and volume, endometrial thickness
 - Uterine shape and fundo-cervical ratio
 - LH and FSH
 - Serum 17-β estradiol

- Skeletal age and bone health
 - Change in bone age/chronological age per year
 - Change in size-adjusted whole body lumbar spine and hip bone mineral areal density (BMAD) (z-score) before and after induction
- Metabolic profile

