6.2 Sample size

Mean (SD) height gain during three years of pubertal induction in the UK clinical trial of Gault et al [26] in which TS girls were treated with a consistent dose of GH has been calculated as 12.2 (3.5) cm. A mean difference of 2.5 cm between transdermal and oral regimens is considered clinically significant, giving a fractional effect size (f) of 2.5/3.5 = 0.71. Using the Lehr formula where $n=21/f^2$ gives the number of patients in each arm of the study required for 90% power at the 5% level [31], the number would be 42. However, given the covariates including age at diagnosis, karyotype, age at starting growth hormone therapy, differing dosage regimens, and use or not of Oxandrolone amongst the enrolled patients, a recruitment target of twice the power calculation, i.e. up to 84 in each treatment arm, is considered desirable so as to adjust for potential confounding factors. Note that this target of 84 in each treatment arm applies to girls undergoing the full 3-year induction period and does not include girls undergoing the shortened induction period.

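### The figure of 84 per arm serves both as the recruitment target and as the number who must complete induction before analysis; the two agree only with zero drop-out

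*Protocol*

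**What the plan says.** Three places in the protocol give the size of the study.

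- **Synopsis, planned size of sample:** "84 patients in each treatment arm – transdermal and oral = 168 total".
- **Section 6.2 (Sample size):** the power calculation gives 42 per arm. This is then doubled: "a recruitment target of twice the power calculation, i.e. up to 84 in each treatment arm, is considered desirable". The stated reason is adjustment for potential confounders. The section adds that "this target of 84 in each treatment arm applies to girls undergoing the full 3-year induction period", so girls on the shortened schedule do not count.
- **Section 4.6 (Data analysis):** the comparisons are made "When the target number of patients has been enrolled (see below)" and, as a further condition, once "a sufficient number (84 in each arm) have completed the full 3-year induction".

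The protocol expects some girls to leave. Table 1 in section 3.2 lists "Percentage drop-outs from either regimen" among the secondary outcomes, section 4.6 reports drop-outs by arm, and section 7.5 has them recorded centrally. No drop-out rate is assumed anywhere.

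Under section 4.1 families choose oral, transdermal or neither, and the choice depends partly on local supply. No allocation ratio is set, and nothing says what happens when one arm reaches its number before the other.

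**The concern.** Section 6.2 counts girls who enter the 3-year induction, with 84 per arm as the upper figure. Section 4.6 counts girls who have finished it, and asks for the same 84. A reader cannot tell whether the planned 168 is a number enrolled or a number of completers.

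Two things are at stake. The first is operational: the condition for starting the analysis cannot be met at the stated size once a girl drops out, and the protocol does not say whether recruitment then continues, for how long, or in which arm.

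The second is the population that the target favours. If the study is counted in completers, there is pressure to fill the count with girls who stayed on their regimen. Staying may differ by route, since acceptability and adherence are among the outcomes compared. Selection on an event after the start of treatment is not removed by propensity matching on baseline factors.

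**Working it through.** **Inputs.** Section 6.2 gives the mean (SD) height gain: it "has been calculated as 12.2 (3.5) cm". It also gives the difference to detect (2.5 cm), 90% power and the 5% level. The drop-out rates and choice proportions below are assumptions, because the protocol gives none.

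**1. The plan's own figure.** Lehr: n = 21/f². With f = 2.5/3.5 = 0.714, n = 41.2; with f rounded to 0.71, n = 41.7. Both round up to 42. Then 2 × 42 = 84 and 2 × 84 = 168. All of this reproduces, so there is no arithmetic error.

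**2. Drop-out.** Enrolment per arm for 84 completers is 84/(1 − d). Completers from 84 enrolled are 84 × (1 − d).

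| Assumed loss d | Enrol per arm for 84 completers | Total | Completers per arm if 84 enrolled | Ratio to 42 |
|---|---|---|---|---|
| 0% | 84 | 168 | 84 | 2.0 |
| 10% | 93.3 → 94 | 188 | 75.6 | 1.8 |
| 15% | 98.8 → 99 | 198 | 71.4 | 1.7 |
| 20% | 105 | 210 | 67.2 | 1.6 |

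The last column shows what loss does to the doubling, which section 6.2 reserves for confounding. If girls leave independently, the chance that all 168 complete is (1 − d)^168: 0.99^168 = 18% at 1% loss, and 0.95^168 = 0.02% at 5% loss.

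**3. Uneven choice.** If a share s chooses the less popular route, 84 enrolled in that arm needs 84/s in total: 84/0.40 = 210, or 84/0.30 = 280, before any loss. If instead the total is held at 168, the smaller arm has 168 × 0.40 = 67 or 168 × 0.30 = 50 girls.

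**4. Does this threaten power?** Two-sided t-test at 5%, difference 2.5 cm, SD 3.5 cm, no adjustment for confounding or centre:

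| Girls analysed | Power |
|---|---|
| 84 v 84 | 99.6% |
| 71 v 71 (15% loss) | 98.8% |
| 50 v 118 (70:30 choice) | 98.8% |
| 25 v 143 | 90.6% |
| 24 v 144 | 89.6% |

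Neither moderate loss nor an uneven split brings unadjusted power near 90%. Equal arms of 84 are not needed for the stated aim.

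**The case against.** The strongest reply is that nothing in the protocol closes recruitment at 84 per arm or at 168. Section 6.2 calls the figure a target that is desirable, and section 4.6 lists enrolment and completion as separate conditions, so the study could keep recruiting until 84 per arm have finished. This stands against any claim that the trigger can never be met. It does not rescue the stated size, because on that reading 168 is no longer the number to be enrolled.

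A reader might also infer that uneven preference blocks the analysis. The target is set per arm, so a less popular route only fills more slowly. It becomes a block only if the total is capped at 168 or the eight-year study period in the synopsis runs out.

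A third tempting inference is that the protocol prescribes a completer analysis, so that girls who stop lose their primary outcome. It does not say so. Section 4.6 fixes when the analysis starts, not who is in it; drop-outs are reported by arm, and section 6.1.2 says adherence problems will be taken into account. The analysis population may properly be set in the statistical analysis plan, which is not shown. What remains is that a target counted in completers invites such selection.

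Finally, the loss and choice proportions are assumed. The inconsistency does not depend on them, since any loss above zero produces it.

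**Conclusion.** The synopsis and sections 4.6 and 6.2 are inconsistent about what 84 per arm means. The number required to complete equals the number to be recruited, with no drop-out allowance and no rule for unequal filling. If recruitment stops at target, one drop-out in either arm leaves the trigger unmet. If it does not stop, 84 completers per arm need 188 to 210 girls in total at assumed losses of 10% to 20%, rather than 168.

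This is an inconsistency in the stated size and trigger, not a calculation error or a shortage of patients. Unadjusted power is 98.8% at 71 v 71 and at 50 v 118, so no extra girls are needed for the stated difference. That rests on the protocol's SD of 3.5 cm and is before any reduction for confounding or clustering by centre, which the documents do not allow one to quantify. The point deserves correction, but the study does not stand or fall by it.

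**What to change.** 1. In the synopsis and section 6.2, state that 168 is the total enrolled on the full schedule (3 or 3½ years). State a drop-out assumption and print the number expected to have an end-of-induction height; at 15%, for example, 168 × 0.85 = 143.
2. In section 4.6, replace the completer condition with a follow-up condition: analyse when the last enrolled girl has reached the planned end of her induction schedule or left follow-up. Tying this to each girl's own schedule, rather than a fixed 36 months, keeps the primary outcome intact for very short girls on the 3½-year schedule.
3. Drop the requirement of exactly 84 in each arm, and say that recruitment continues to the total whichever arm fills first.
4. Keep every girl who started in her initial regimen group, using her routine clinic height at the planned end of induction where available. Height is already an essential measurement in Table 4.
5. In section 5, where data are sent at the end of each year of the chosen regimen, add that this height is still reported for girls who have stopped the regimen.

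The cost is wording in the synopsis and sections 4.6, 5 and 6.2, plus a small reporting task for centres whose patients stop early. No additional patients are needed. The downside is that the stated number analysed becomes somewhat smaller than 84 per arm, which narrows the margin kept for confounding.

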5 STUDY SETTING

This is a multicentre, international study which includes the UK. The study setting will be in endocrine clinics and centres within the UK, other European countries, and beyond. Treatment administration and data collection will be carried out as indicated above. A single European centre will receive

Transdermal vs oral 17β -estradiol protocol Version 1.0 July 12^{th} 2020

anonymised data from study participants at enrolment and at the end of each year of the pubertal induction regimen chosen.

Participating centres and countries are likely to have at least some ESPE members. Centres must have facilities for recording the essential data required for good management in TS (see section 5.5).

6 SAMPLE AND RECRUITMENT

6.1 Eligibility Criteria

6.1.1 Inclusion criteria

- Karyotype-proven Turner syndrome
- Pubertal induction for primary ovarian failure required (FSH > 10 IU/L)
- Age ≥ 11 years at time of induction
- Written informed consent/assent, as applicable

6.1.2 Exclusion criteria

There are no formal exclusion criteria. However, note will be taken in the analysis of patients with accompanying health problems such as hypothyroidism, coeliac disease and inflammatory bowel disease, all of which have an increased prevalence in TS. Moreover, problems with adherence/compliance will also be taken into account when analysing the data.

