1 BACKGROUND

Turner syndrome (TS) is a condition in which there is loss of the second sex chromosome (either X or Y) and/or abnormality of the second X chromosome in at least one major cell line in a phenotypic female. Features include short stature and primary ovarian insufficiency, accompanied by typical phenotypic traits and a variety of associated cardiac and renal malformations in a minority [1,2].

TS carries a significant morbidity and mortality [3,4]. Long-term health consequences for cardiovascular disease and osteoporosis are particularly important. Problems such as aortic dissection (arising particularly in girls with previously repaired aortic coarctation or bicuspid aortic valve), hypertension, atheroma and increased risk of metabolic syndrome [5,6,7,8,9,] give rise to a marked increase in mortality rate (standardised mortality ratio 3) and a life expectancy 13 years less than the general population, a finding similar to patients with diabetes. However, since TS has a relatively low prevalence, affecting about 1 in 2000 live female births [1], there is little awareness of the condition and its implications.

Appropriate, physiological sex steroid replacement is essential in the optimal management of patients with TS from puberty through to the age of normal menopause. Estrogen induction of puberty is usually required in TS, a retrospective Italian study showing that spontaneous onset of periods (menarche) occurred in only 84 of 522 (16.1%) patients [10]. Puberty is a highly important process both physically and psychologically. Over 50% bone mineral accrual occurs during puberty & the early post-pubertal years [11]. Moreover timely pubertal induction is important for self-esteem, psychosexual development and quality of life.

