4.1 Identification of patients and enrolment process (see Figure 1)

At 10-11 years clinicians should, as part of normal clinical practice, assess the need for pubertal induction by measuring the hormone follicle-stimulating hormone (FSH), levels of >10 IU/L indicating a degree of primary ovarian failure necessitating estrogen replacement.

Clinicians from European countries and beyond who wish to participate in the study will counsel the families of girls requiring pubertal induction as to the options. These include either of the oral and transdermal regimens agreed and recommended by the TSWG of ESPE; and alternative regimens.

This is an open, non-randomised study comparing two regimens which are regarded as best practice. Clinicians will be asked to help families make an informed choice regarding either or neither of the oral or transdermal regimens recommended by TSWG. Choice will depend partly on the availability of the recommended transdermal or oral 17β -estradiol preparations, but clinicians are entitled to request appropriate, treatment from their hospitals and pharmacies which comply with Cincinnati and UK guidelines [13,14]. In the event of a family choosing either of the TSWG-recommended regimens, written informed consent and assent will be requested by the clinician for participation in the study and the European central registry will be contacted.

This consent is for anonymised data (with the exception of date of birth, which is required for analysis) before, during and after pubertal induction to be sent to the designated European centre and entered into an independent ESPE-approved database under the supervision of an ESPE TSWG member trained in Good Clinical Practice.

In the UK, NHS Research Ethics Committee (REC) & Research and Development (R&D)/HRA approvals will be sought, enabling participating centres to recruit and enroll patients into the study.

Outside the UK, participating centers will need to follow their national regulatory procedure and gain ethical approval for patients and families to give written consent.

Since the proposal is not a randomised clinical trial, but an observational cohort study it should not need to be registered as the former. Any medications given for pubertal induction would be prescribed and funded in the usual way for the country concerned.

4.2 Age, duration and protocols for oral and transdermal 17β-estradiol induction of puberty in TS

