Induction of puberty will be from 11 years. Specific age of beginning induction, and duration of induction are at the discretion of the clinician in consultation with the family. Initiation of treatment in eligible patients should normally begin at between 11-12 years, consistent with the Cincinnati and UK guidelines [13,14]. Pubertal induction should normally be carried out over a 3-year period. However, a later induction age will be necessary in girls presenting >12 years. Also, a faster induction period (e.g. 2 years) should be considered in girls who are older (e.g. >14 years) at the time of starting induction due to late diagnosis.

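### Prior estrogen is never recorded and entry is not limited to prepubertal girls, while breast and uterine outcomes are end values, so development before the regimen can pass as a route effect

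*Protocol*

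**What the plan says.** **Entry.** Section 6.1.1 asks for a proven karyotype, consent, "Age ≥ 11 years at time of induction" and "Pubertal induction for primary ovarian failure required (FSH > 10 IU/L"). Section 6.1.2 adds: "There are no formal exclusion criteria". No breast stage, estrogen-naive condition or upper age is set. Section 4.1 reads the FSH threshold as "levels of >10 IU/L indicating a degree of primary ovarian failure necessitating estrogen replacement", which leaves room for partial ovarian function. Section 4.2 expects that "a later induction age will be necessary in girls presenting >12 years".

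**Data collected.** In Table 4, breast and pubic hair stage before induction is essential. Pelvic ultrasound, bone age and serum estradiol before induction are only desirable. The concurrent-treatment item covers GH, L-T4 and oxandrolone. The text after the table asks for a detailed GH history and any oxandrolone use, but not for earlier estrogen.

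**Outcomes.** In Table 1 the primary outcome is the height increase over the induction period. The breast outcome is whether stage 4 or 5 has been reached. The uterine measures stand under "Uterine health and sex hormone profile at the end of induction". Aortic root, bone density and height SDS are defined as changes between start and end.

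**Adjustment.** Section 4.6 gives as examples of confounders "45,X karyotype, midparental height, height at the beginning of pubertal induction, duration of prior GH treatment, GH responsiveness and treatment or not with oxandrolone", and then uses Directed Acyclic Graphs to settle the set for each outcome.

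**The concern.** The study asks which route induces puberty better, and families choose the route, partly according to which preparations are available locally. Nothing in the design balances earlier pubertal development or earlier estrogen between the arms.

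If one arm holds more girls who have already developed or been treated, three things follow. Its breast and uterine results look better, because end status credits the regimen with what was there at the start. Its height gain may look worse, because less growth may remain. And the part due to earlier estrogen cannot be separated afterwards, because nobody asked about it.

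**Working it through.** **1. The plan's own figure.** Section 6.2 uses an SD of 3.5 cm and a difference of 2.5 cm. Lehr's formula gives 21 / (2.5/3.5)² = 41.16, rounded up to 42 per arm, as stated. Power is 90.5% at 42 per arm and 99.6% at 84, before any adjustment. The sample size is not in error.

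**2. Can such girls enter, and would the data show it?**
- Puberty already begun: nothing bars entry, but the essential baseline breast stage shows it.
- Estrogen already given: nothing bars entry, and no item in Table 4 shows it. A single baseline estradiol value, itself only desirable, does not establish past exposure.

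**3. Breast outcome.** Let a share p of an arm enter already at stage 4 or above, and let the other girls reach it with the same probability r in both arms. The arm's rate is p + (1 − p)r, so the spurious difference between arms is (imbalance in p) × (1 − r). With an assumed imbalance of 10 points:
- r = 0 gives 10 points, the ceiling.
- r = 0.8 (assumed) gives 0.10 × 0.2 = 2 points.
- r = 1 gives 0.

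The protocol gives neither p nor r.

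**4. Uterine outcomes.** The end value is the starting value plus growth on the regimen. Without the starting value in the analysis, a difference between arms at the start carries into the comparison. A pre-induction scan is already recommended, so the correction is available where it was done.

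**5. Height gain.** Suppose pre-exposed girls gain D cm less during induction. Then bias = (difference in their share between arms) × D.

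| Imbalance | D = 1 | D = 2 | D = 4 | D = 6 |
|---|---|---|---|---|
| 0 points | 0 | 0 | 0 | 0 |
| 10 points | 0.1 cm | 0.2 cm | 0.4 cm | 0.6 cm |
| 20 points | 0.2 cm | 0.4 cm | 0.8 cm | 1.2 cm |

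Against 2.5 cm this runs from 4% (0.1/2.5) to 48% (1.2/2.5). D and the imbalance are assumptions throughout.

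**6. Power.** With shares p₁ and p₂, pooled SD = √(3.5² + ½[p₁(1 − p₁) + p₂(1 − p₂)]D²).
- 10% versus 30%, D = 4: √(12.25 + 0.15 × 16) = 3.83 cm. Required n is 50 per arm, and power at 84 is 98.8%.
- 20% in both arms, D = 6: √(12.25 + 0.16 × 36) = 4.24 cm. Power at 84 is about 97%.

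The larger sample absorbs the extra spread. It does not remove the bias, which is the same at 42 or 84 per arm. Section 6.2 doubles the sample so that confounders can be adjusted for, and that works only for confounders that are recorded.

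**The case against.** The case against is substantial, and most of it limits the point.

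- **Height.** A reader might infer that height gain includes growth from before the regimen. It cannot: it is measured from the start of induction. Only the confounding route, less growth left, remains.
- **Puberty already begun.** A reader might infer that this is invisible to any later analysis. It is not, because baseline breast stage is essential. Earlier estrogen large enough to matter would also show there in part, but not fully and not as a cause.
- **Confounder list.** The list in section 4.6 consists of examples, and the graph step leaves the set open. Baseline breast stage can still be added in a statistical analysis plan, so its absence from the list is not an error. Prior estrogen is different: a graph may identify it, but an uncollected variable cannot enter a model.
- **Who enters.** The need for induction is itself a filter. Section 4.2 attributes older starts to late diagnosis, not earlier treatment. Two-year inductions are analysed separately and do not count towards the 84. This reduces the number affected but not to zero, since the short course is discretionary and puberty that began and stalled can still need induction.
- **Prevalence.** The Background states that "spontaneous onset of periods (menarche) occurred in only 84 of 522 (16.1%) patients". A reader might take this as the share of affected entrants. It describes Turner patients generally, not girls judged to need induction, and shows only that some ovarian function is not rare.
- **Direction.** The protocol gives no reason why either route would attract these girls, so the bias could be nil or run either way.

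**Conclusion.** The point holds in a limited form. Entry is open to part-developed and previously treated girls, prior estrogen is not collected, and the breast and uterine outcomes are end values in a table that uses change from the start for other measures. The gap in data collection is the part that no later analysis plan can close.

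The effect on height is a possible confounding of unknown size: 0.1-1.2 cm against 2.5 cm under assumed deficits of 1-6 cm and imbalances of 10-20 points, before any adjustment, and zero if the arms are balanced. Power is not affected in any way that matters. The documents do not support the stronger conclusion that the main analysis must be confined to girls at an early breast stage without prior estrogen: any such cut-off is debatable and would narrow a deliberately pragmatic study.

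**What to change.** - **Table 4, essential baseline items:** add any prior estrogen treatment (yes/no, type, months), and spontaneous breast development or menarche (yes/no). These must be on the form from enrolment, since retrieving them years later across countries would be unreliable.
- **Section 4.6:** include baseline breast stage and prior estrogen among the confounders for the height, breast and uterine outcomes.
- **Breast and uterine outcomes:** analyse breast outcome adjusted for baseline stage, and uterine size adjusted for the pre-induction scan where there is one.
- **Sensitivity analysis:** repeat these comparisons in girls with no prior estrogen and no breast development at the start.

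The cost is two history questions, one or two extra covariates, and fewer girls in the baseline-adjusted uterine analysis, because the baseline scan is only desirable. Eligibility and treatment are unchanged.
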